11.4 Management and follow-up of AEs and SAEs

Medical follow-up (such as history, physical examination, laboratory testing and/or treatment) may be necessary if a participant experiences an AE.

All AEs and SAEs recorded for this study, regardless of relationship to IP, should be followed until resolution or stabilisation.

Participants experiencing SAEs should be followed clinically until their health has returned to baseline status or until all parameters have returned to normal, are stabilised, or have otherwise been explained.

11.5 Reporting of Serious Adverse Events

Investigators and other site personnel must report SAEs to MCRI's representative within 24 hours of becoming aware of the SAE, regardless of causality.

STUDY CONTACTS AND PROCESSES FOR REPORTING SERIOUS ADVERSE EVENTS ARE DESCRIBED IN THE STUDY REFERENCE MANUAL.

Follow-up information on SAEs must also be reported by the investigational site within the same time frame. If a non-serious AE becomes serious, this and other relevant follow-up information must also be provided within 24 hours.

All SAEs will be recorded in the participant records and the CRF. MCRI or designee is responsible for informing the regulatory authorities of the SAE as appropriate.

The investigator must notify their Independent Ethics Committee (IEC) of any SAEs within the time period specified by the IEC. MCRI or designee is responsible for informing other relevant IECs.

12 STUDY OVERSIGHT

12.1 Medical Monitors

The Medical Monitor is an appropriately qualified, designated physician who will be available to advise on trial related medical questions or problems, without other direct involvement with trial participants. The Medical Monitor will be available to respond to questions from the investigators about study eligibility, abnormal assessments, participant follow-up, assistance with AE and SAE assessment, concomitant medications and criteria for delay of IP. The contact details for the Medical Monitor are available in the SRM.

12.2 Steering Committee

The Steering Committee (SC) is a MCRI group and may include non-MCRI personnel as invited. The SC will provide oversight of the trial to review recruitment rates, site progress, and protocol compliance. The SC's responsibilities will be documented and will include input into protocol amendments, contact with study investigators to promote recruitment and high quality data, review, recommendation and implementation of major protocol changes, and implementation of DSMB recommendations.

12.3 Data Safety Monitoring Board

An independent DSMB will be established prior to recruitment start, with appropriate charter that defines its roles and responsibilities. The DSMB will monitor accruing trial safety results at intervals throughout the study. The main purpose of the DSMB will be to protect the interests of the participants included in the trial.

The charter will specify the intervals for formal DSMB meetings.

The DSMB will convey to MCRI their recommendations as to whether the trial may continue as planned or if the trial should be modified or stopped. The final decision on whether the study should be modified or stopped will be the responsibility of MCRI. Any decision to modify or stop will be communicated to investigators and regulatory agencies by MCRI (or their representatives).

13 STATISTICS AND DATA EVALUATION

The statistical analysis principles described below will be supplemented by a comprehensive statistical analysis plan (SAP) which will be finalised before the database is locked. Any changes to the statistical plans will be described and justified in the final report.

13.1 Sample Size Assumptions

With the high titre RV3-BB neonatal vaccine schedule as the active control arm, the sample size is calculated to demonstrate the non-inferiority of the lower titre vaccine arms with respect to the proportion of participants who have a serum IgA response 4 weeks after 3 doses of vaccine. A non-inferiority margin of 20% for the difference between arms will be used. The primary analysis is based on the per protocol population defined as participants who receive all 3 doses and have no major protocol violations. Thirty percent of participants

are expected to be excluded from the PP population due to death, study withdrawal, loss to follow-up, or study non-compliance. Among those in the PP population, a 50% response probability is assumed for the active controls. Based on a one-sided 0.025 level score test with 90% power under the alternative of no difference in response probabilities, 172 participants per arm are required for a total sample size of 688 participants.

Non-inferiority of the lower titre vaccine will also be assessed in the intention to treat population. The cumulative probability of response by 18 weeks of age will be estimated by the Kaplan-Meier method for each vaccine arm. The difference between high and low titre arms in the cumulative probabilities and its 95% confidence interval will be calculated. If the upper bound of the confidence interval is below 20%, non-inferiority of the lower titre vaccine will be demonstrated.

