Sample Size and Statistical Analyses	With the high titre RV3-BB neonatal vaccine schedule as the active control arm, the sample size is calculated to demonstrate the non-inferiority of the lower titre vaccine arms with respect to the proportion of participants who have a serum IgA response 4 weeks after 3 doses of vaccine. A non- inferiority margin of 20% for the difference between arms will be used. The primary analysis is based on the per protocol population defined as participants who receive all 3 doses and have no major protocol violations. Thirty percent of participants are expected to be excluded from the per protocol (PP) population due to death, study withdrawal, loss to follow-up, or study non-compliance. Among those in the PP population, a 50% response probability is assumed for the active controls. Based on a one- sided 0.025 level score test with 90% power under the alternative of no

difference in response probabilities, 172 participants per arm are required
for a total sample size of 688 participants.
Non-inferiority of the lower titre vaccine will also be assessed in the
intention to treat population (ITT). The cumulative probability of response
by 18 weeks of age will be estimated by the Kaplan-Meier method for each
vaccine arm. The difference between high and low titre arms in the
cumulative probabilities and its 95% confidence interval will be calculated.
If the upper bound of the confidence interval is below 20%, non-inferiority
of the lower titre vaccine will be demonstrated.

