8.1.1 Sample size

With the high titre RV3-BB neonatal vaccine schedule as the active control arm, the sample size is calculated to demonstrate the non-inferiority of the lower titre vaccine arms with respect to the proportion of participants who have a serum IgA response, 4 weeks after 3 doses of vaccine. A non-inferiority margin of 20% for the difference between arms will be used.

The primary analysis is based on the per protocol population defined as participants who receive all 3 doses of RV3-BB and have no major protocol violations. Thirty percent of participants are expected to be excluded from the PP population due to death, study withdrawal, loss to follow-up, or study non-compliance. Among those in the PP population, a 50% response probability is assumed for the active controls. Based on a one-sided 0.025 level score test with 90% power under the alternative of no difference in response probabilities, 172 participants per arm are required for a total sample size of 688 participants.

8.1.2 *Multicentre studies*

Approximately 688 babies will be randomised across three sites in Malawi. Study visits will be conducted at the sites or at participant homes.

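### At the planned 30% exclusion, 172 per arm leaves 120 in the per-protocol set and about 88% power, not the stated 90%

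*Protocol*

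**What the plan says.** Protocol 13.1 takes the high-titre neonatal arm as the active control and compares each lower-titre arm with it on the proportion with a serum IgA response after three doses. It sets the design values as follows:

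- Margin: "A non-inferiority margin of 20% for the difference between arms will be used".
- Response: "a 50% response probability is assumed for the active controls", with the lower-titre arm assumed equal.
- Test and power: "Based on a one-sided 0.025 level score test with 90% power under the alternative of no difference in response probabilities".

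The conclusion drawn is "with 90% power under the alternative of no difference in response probabilities, 172 participants per arm are required for a total sample size" of 688. The synopsis repeats it ("difference in response probabilities, 172 participants per arm are required"), and so does SAP 8.1.1.

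On losses, SAP 8.1.1 says: "Thirty percent of participants are expected to be excluded from the PP population due to death, study withdrawal, loss to follow-up, or study non-compliance". Protocol 13.2 and SAP 6.1.4 place the primary analysis on the PP set. Neither document gives the evaluable number per arm or the formula used to inflate it.

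**The concern.** If 30% of those randomised are excluded, the PP set is 70% of 172, or about 120 per arm. A non-inferiority comparison at 50% response with a 20-point margin needs roughly 130 per arm for 90% power, so the stated number and the stated exclusion rate do not fit together.

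What is at stake is the accuracy of the power claim for the primary comparison. The shortfall is already present at the exclusion rate the plan itself expects, before any further loss from the PP set. If a lower-titre arm narrowly misses the margin, readers will judge that result against a 90% figure that the design does not deliver. Because the same text stands in the synopsis, the protocol body and the SAP, it is likely to be carried into the study report.

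**Working it through.** **Inputs** (Protocol 13.1, synopsis and SAP 8.1.1): response 0.50 in both arms; margin 0.20; one-sided alpha 0.025 (z = 1.960); power 90% (z = 1.2816); equal allocation; 30% excluded from the PP set; 172 randomised per arm.

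**1. Evaluable number per arm for 90% power**

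- Score formula. With a true difference of zero at 0.50, the response rates constrained to the null are 0.6 and 0.4. The null variance term is 2 × 0.6 × 0.4 = 0.48 and the alternative term is 2 × 0.5 × 0.5 = 0.50.
  n = (1.960 × √0.48 + 1.2816 × √0.50)² / 0.20² = 128.2, so **129**.
- Unpooled variance.
  n = (1.960 + 1.2816)² × 0.50 / 0.20² = 10.507 × 0.50 / 0.04 = 131.3, so **132**.

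**2. Number to randomise when 30% are excluded**

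- Score: 129 / 0.70 = 184.3, so **185** per arm (740 in total).
- Unpooled: 132 / 0.70 = 188.6, so **189** per arm (756 in total).
- The smallest PP number at which the exact power of the score test passes 90% is 127, and 127 / 0.70 = 181.4, so 182 per arm.

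Against the stated 172, the two formulas give 13 to 17 more per arm (52 to 68 in total), or 7.6% to 9.9% above the plan.

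**3. Where 172 could come from**

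- 132 × 1.30 = 171.6, so 172: the loss multiplied on instead of divided out.
- 129 / 0.75 = 172: the score test with 25% exclusion.
- Variance taken at rates of 50% and 30%: 10.507 × (0.25 + 0.21) / 0.04 = 120.8, and 120.8 / 0.70 = 172.6. This is close, but it uses neither the constrained score variance nor the variance at the stated alternative.

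None of these is the stated score test with 30% excluded. The documents do not show which was used.

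**4. Power with 172 randomised**

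172 × 0.70 = 120.4, so 120 per arm in the PP set.

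- Score formula: Φ[(0.20 × √120 − 1.960 × √0.48) / √0.50] = **88.1%**.
- Unpooled: Φ[0.20 / √(0.50/120) − 1.960] = **87.3%**.
- Exact binomial enumeration of the score test: **89.0%**. The Newcombe-Wilson interval named in SAP 9.1.2 also gives 89.0%.

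Exact power moves in a saw-tooth, so the value at 120 should not be read too finely:

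| PP per arm | Exact power, score test |
|---|---|
| 118 | 86.6% |
| 120 | 89.0% |
| 124 | 88.6% |
| 126 | 89.0% |
| 127 | 90.6% |

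**5. Exclusion rate at which 172 gives 90%**

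- Score formula: 1 − 129/172 = 25%.
- Unpooled: 1 − 132/172 = 23%.
- Exact score test: 1 − 127/172 = 26%.

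**The case against.** The strongest case against is about size and emphasis.

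- **Exact power.** The exact power of the named test is 89.0%, so the shortfall may be only one point; the 87.3% belongs to a variance the protocol does not name. This is fair, but 120 sits at a local high of the saw-tooth and the exact value falls to 86.6% at 118. A summary of about 88% is reasonable, and no method used here gives 90% at 120.
- **The threshold.** The 25% limit comes from the formula. Exact power passes 90% at 127 per arm (26% exclusion) for the score test, and at 125 (90.3%, 27% exclusion) for the Newcombe-Wilson interval. That stands, so 25% should be given as a rate at which 90% is met, not as the only one.
- **The cause.** That the loss was multiplied by 1.30 is an inference. It needs the unpooled 132, since the score value gives 129 × 1.30 = 168, and other routes lead to or near 172. That stands too. The finding does not depend on the cause.
- **Consequence.** The 30% is a forecast and 688 is described as approximate. Non-inferiority is decided by the upper confidence bound, not by planned power. SAP section 5 already reports laboratory findings on cord samples, so the planned power could no longer change the trial's size when that text was written. All true. It limits the remedy to a correction of wording but does not make the stated power right.

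**Conclusion.** The concern holds. On the plan's own inputs, 172 per arm with 30% excluded leaves 120 per arm in the PP set and gives about 88% power per comparison (87.3% to 89.0% by method), against 90% stated. The loss is 1.0 to 2.7 percentage points. Meeting the stated 90% would take 185 to 189 randomised per arm by the two formulas.

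This is a definite but modest arithmetic error in the primary sample-size statement; it does not make the trial seriously underpowered. The result assumes 50% true response in both arms, a 30% loss in each arm, and power reckoned separately for each lower-titre arm against the high-titre arm. No conclusion about how the error arose is needed.

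**What to change.** Restate the figure in the synopsis, Protocol 13.1 and SAP 8.1.1, for example: *172 per arm gives about 88% power per comparison if 30% are excluded from the PP set, and 90% if exclusions do not exceed 25% (score test).* Adding the evaluable numbers behind it (129 needed for 90%, 120 expected) would let a reader check it.

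The cost is one sentence in three places and a slightly less favourable power figure. Enrolment, margin, analysis sets and decision rule stay as they are. If the protocol is no longer being amended, the correction can go into the SAP and the final report, where Protocol section 13 already requires changes to the statistical plans to be described and justified.

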13.2 Analysis Sets

The following sets will be used for the statistical analyses:

Full analysis set (FAS): All participants randomised into the study. Participants will be analysed according to treatment to which they were randomised. Immunogenicity analyses performed in the FAS are considered supportive.

Safety set: All randomised participants who received at least one dose of IP. Participants will be analysed according to the treatment received.

Intention-to-treat (ITT) set: All randomised participants who received at least one dose of IP and have an evaluable baseline and post-baseline blood sample. Participants will be analysed according to the treatment to which they were randomised. Supportive immunogenicity analysis will be performed in the ITT set.

Per-protocol (PP) set: All participants from the ITT population who completed the study in compliance with the protocol and who reported no major violation of the study protocol. Participants will be analysed according to the treatment to which they were randomised. The final decision to exclude a participant from the PP set will be taken during a blinded data review meeting before database lock. Primary analyses are performed on the PP set.

13.3 Data Analysis Considerations

All immunogenicity and safety data will be listed and summarised using descriptive statistics by treatment group and nominal time. The descriptive summary for the categorical variables will include counts and percentages. The descriptive summary for the continuous variables will include means, medians, standard deviations and minimum and maximum values. Where possible, data from participants who withdraw prematurely from the study will be included in any analysis. Further details on the handling of withdrawals and/or missing data will be specified in the SAP.

All statements of statistical significance will be based on a two-sided test at the 5% level of significance, unless stated otherwise. Further details will be specified in the SAP.

The baseline value for each clinic assessment will be the last pre dose value obtained.

Full details of the statistical analyses will be presented in the SAP. Any deviations from the planned analyses detailed in the protocol will be documented in the SAP and final study report. If the study is prematurely discontinued, all available data will be listed and a review will be carried out to determine which statistical analyses are considered appropriate.

13.3.1 Demographics and Baseline Data

Demographic and baseline characteristics will be listed and summarised by treatment arm.

13.3.2 Immunogenicity Analyses

13.3.2.1 Definition of baseline IgA for the calculation of vaccine take

Due to the timing of the blood tests, baselines for serum anti-rotavirus IgA are defined differently for participants in the neonatal vaccine schedule and the infant vaccine schedule. Baseline serum anti-rotavirus IgA in the neonatal vaccine schedule is defined as the measurement from the cord blood. In the infant vaccine schedule baseline is defined as the measurement from analysis of serum collected prior to the second dose, although the measurement from the cord blood may be used if there are no data on IgA following the first dose of IP.

Further details of the analysis of secondary endpoints will be described in the SAP. Details about multiplicity and Type I error for secondary endpoints will be included in the SAP.

13.4 Safety Data

13.4.1 Extent of exposure

The number of participants exposed to study treatment will be summarised by treatment received.

13.4.2 Adverse events

AE data will be listed individually and incidence of AEs summarised by system organ class and preferred terms within a system organ class for each treatment group. When calculating the incidence of AEs, each AE, based on preferred terminology defined by Medical Dictionary for Regulatory Activities (MedDRA; Version 13.1, or later), will be counted only once for a given participant. A summary of the number and percent of participants with the following treatment emergent AEs will be displayed by treatment groups:

- All AEs
- IP related AEs
- Severe AEs
- SAEs
- AEs leading to permanent discontinuation of IP.

13.4.3 Other safety measures

Continuous variables will be summarised along with the change from baseline at each time point by treatment group. Other variables will be summarised as appropriate to the data.

14 DATA MANAGEMENT

Data collection and entry into the CRF will be completed by authorised study site personnel designated by the Investigator. Appropriate training and security measures will be completed with the Investigator and all authorised study site personnel prior to the study being initiated and any data being entered into the system for any study participants.

All data must be entered in English. The CRFs should always reflect the latest observations on the participants participating in the trial; therefore, the CRFs are to be completed as soon as possible after the participant's visit. The Investigator must verify that all data entries in the CRFs are accurate and correct. If some assessments are not done, or if certain information is not available or not applicable or unknown, this should be indicated in the CRF. The Investigator will be required to sign off on the clinical data.

The study monitor/Clinical Research Associate (CRA) will review the CRFs and evaluate them for completeness and consistency, and compare them to the source documents to ensure that there are no discrepancies between critical data. All entries, corrections and alterations are to be made by the responsible Investigator or designee. The CRA cannot enter data into the CRFs. Once data in the CRF have been entered, corrections to the data fields will be audit trailed, meaning that the reason for change, the name of the person who performed the change, together with time and date of the change, will be logged. Roles and rights of the site personnel responsible for entering the clinical data into the CRF will be determined in advance. If additional corrections are needed, the responsible CRA or Data Manager will raise a query. The appropriate investigational staff will answer queries. This will be audit trailed, as described above.

The CRF is essentially a data entry form and should not constitute the original, or source document. Source documents are all documents used by the Investigator or hospital that relate to the participant's medical history, that verify the existence of the participant, the inclusion and exclusion criteria and all records covering the participant's participation in the study. They may include, but are not limited to, laboratory reports, ECG results, imaging reports, pharmacy dispensing records, hospital records, participant files, etc. For this study, Study Reminder Card and Diarrhoea Logs will be considered source documents.

The Investigator is responsible for maintaining source documents. These will be made available for inspection by the CRA at each monitoring visit.

A CRF will be completed for all participants who are screened.

15 TRIAL MANAGEMENT

15.1 Contacts

Details of study sites, investigators, Medical Monitors, CRAs, and MCRI and designee contacts can be found in the SRM.

15.2 Quality control and Quality Assurance

15.2.1 Monitoring

Study monitoring will be performed in accordance with applicable regulations, International Conference on Harmonisation (ICH) Good Clinical Practice (GCP), and MCRI and designee SOPs.

Before the start of the trial, a representative of MCRI or designee will contact the investigational site to ensure facilities are adequate and discuss responsibilities with the site staff with regards to following the protocol and regulatory and ethical requirements.

During the trial, a CRA from MCRI or its designee will regularly contact and visit the site to monitor study progress, confirm protocol, regulatory and ethical adherence, confirm data accuracy and provide information and support.

A separate unblinded study monitor will conduct monitoring visits at the pharmacy. This monitor will be unblinded to the treatment allocation of participants through their contact with pharmacy personnel and records. The nominated unblinded monitor will ensure that accountability and dispensing records are adequately maintained and ensure that appropriate storage conditions for the vaccine are maintained.

The PI agrees to allow the CRA direct access to all relevant documents, including electronic records, and to allocate their time and the time of their staff to the CRA to discuss findings and any relevant issues.

Site staff will be provided with CRA and back up contact details in the event they have queries or require assistance.

15.2.2 Audits and Inspections

An audit is a systematic and independent examination of trial related activities and documents to determine whether the evaluated trial related activities were conducted, and the data were recorded, analysed and accurately reported according to the protocol, MCRI's SOPs and those of MCRI's designees, GCP and the applicable regulatory requirements.

Authorised representatives of MCRI, its designee, a regulatory authority, or the IEC may visit the centre to perform audits or inspections. The investigator should contact MCRI or designee immediately if they are contacted by a regulatory agency about an inspection at their centre. If an audit or inspection occurs, the PI, site coordinating investigators, and institutions agree to allow the auditor/inspector direct access to all relevant documents and allocate their time and the time of their staff to the auditor/inspector to discuss findings and any relevant issues.

